In a recently completed early feasibility study (ARGOS-01), six glaucoma patients (4 POAG and 2 NPG) at a single university eye clinic in Germany had an earlier version of the ARGOS-IO pressure sensors implanted in the ciliary sulcus concomitantly to cataract surgery. Promising concurrence was seen between IOP profiles obtained with ARGOS-IO, GAT and DCT over the 12 months follow-up period and the ARGOS-IO system was easily used by the patients in the home setting. However, after two fibrin reactions classified as procedure-related SAEs were observed, as were multiple adverse events possibly caused by the size and/or form of the implant, the sponsor stopped the study to investigate the cause.

Analysis of an extensive databank of eye MRIs, obtained from MRI Research Inc., a company supported by the American National Institute of Health National Eye Institute, demonstrated that the ciliary sulcus undergoes a distortion in the first months following cataract extraction. This distortion, which is extenuated by the use of single piece IOLs such as those received by all patients in the

 Implantata Ophthalmic Products GmbH	Clinical Investigation Report ARGOS-KP01	Revision A Page 18 of 114
--	---	----------------------------------

ARGOS-01 study, caused a radial force to be exerted on the ARGOS-IO pressure sensor. In vitro testing was then conducted using a tool specially designed to mimic such pressure in a controlled manner. It was determined that when exposed to such force, the original ARGOS-IO pressure sensor prototype produces aberrant pressure readings and develops a curvature in its horizontal plane.

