As a result of these tests and the ARGOS-01 study, modifications were made to the form of the device and the implantation procedure to improve the device's safety profile. The implant thickness was reduced from 0.9 mm to 0.5 mm overall, tapering to a rounded outer edge of only 0.1 mm, and haptics were added to the device to better maintain its positional stability and to reduce mechanical stresses of the sensor on the eye. In addition, four haptic arms and two allantoid protrusions on the posterior surface of the ring were added to the ring to improve its positional stability, facilitate unfolding and better distribute pressure on the ring. When subjected to radial force, the redesigned sensor ring did not show the abnormalities in pressure readings or the plane distortions seen in the earlier version. The implant is also now available in three different diameters to allow selection of the implant size that best fits the individual participant. Related procedural changes, including the use of a cartridge injector similar to those used to insert foldable IOLs to insert the implant and first use of the sensor at 30 days post-surgery instead of at day 1 to 3 as in the previous study, are expected to reduce potential stress to the patients' anterior chambers during surgery and the initial post-surgical period. Together, these changes are expected to reduce irritation of the iris and pressure drifting observed in the ARGOS-01 study.

Due to the unique form of the human eye, and the exacting nature of the fit, it is not possible to assess the effects of the design modification in animals.

In May 2017, the ARGOS-IO system got the CE approval as intraocular pressure sensor for measurement of intraocular pressure in patients with primary open angle glaucoma due to the ARGOS-02 study. This clinical trial investigated the safety and performance of the ARGOS-IO systems in patients with primary open angle glaucoma undergoing phacoemulsification and IOL implantation for cataract and received ARGOS-IO implants in an add-on procedure. 22 patients were enrolled and their eye condition and IOP were followed over a course of 12 months. The ARGOS-IO measurements showed an excellent level of concordance to the conventional Goldmann Applanation tonometry and no device related serious adverse events were recorded (Implantata, 2017).

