One objective of this study was to verify the device's accuracy in the patient population. Patients will benefit from a continual long-term monitoring of IOP independent from visits to the ophthalmologist. The Sponsor plans to develop an internet platform that will permit the physician to remotely access information from individual readings, allowing patients' IOP to be monitored by the treating physician between office visits. This will permit a more rapid response to changes in IOP and a better fine-tuning of treatment protocols.

Because of the high risk of critically IOP values possible in BKPro patients, glaucoma may progress more rapidly as at open angle glaucoma patients, which requires an even closer monitoring regimen. An additional effect may be improved adherence to prescribed treatment regimens. The potential consequences of poor IOP control are serious and can lead to irreversible loss of vision and accompanying handicap. Patient self-measurement is expected to motivate better compliance with the treatment regimen, thereby facilitating improved IOP control and optimizing long-term outcome.

The ARGOS-KP01 clinical trial was conducted to address these questions:

Compatibility with Boston-Keratoprosthesis

The ARGOS-KP01 study confirmed that it possible to implant a BKPro and ARGOS-IO sensor without mutual interference.

Irritation, Inflammation of Eye, Iris Pigment Abrasion

Does the implant cause irritation, inflammation and pigment abrasion?

 Implantdata Ophthalmic Products GmbH	Clinical Investigation Report ARGOS-KP01	Revision A Page 101 of 114
---	---	-----------------------------------

- Implant surface material has history as IOL material for ocular implantation, with well-known biocompatibility properties; material surface is soft, edges are rounded and smooth, possible small material flashes are soft and atraumatic
- In ARGOS-KP01 trial, the ARGOS-IO device was found to be safe and well tolerated within the eye. No higher levels of irritation, inflammation and pigment abrasion were observed compared to standard Boston Keratoprosthesis implantation and were manageable under standard of care.

Accuracy, precision and sensor drift

Does the ARGOS-IO device exhibit acceptable levels of accuracy and precision?

- Accuracy, precision and sensor drift have been tested and validated in bench tests and in animal trials

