- The ARGOS-IO device was compared to finger palpation (the current gold standard in BI-KPro patients) within this clinical trial and showed a positive statistically significant difference of telemetric IOP measurements between the finger palpation categories (soft hypertonic, normal, borderline, hypertonic).
- ARGOS-KP01 trial has shown that the human anatomy does not have an impact on the accuracy of the device. It is recommended to re-calibrate the device once a year and following ocular surgery.

Usability

The patient acceptance of the ARGOS-IO system at home was very good, showing a very high overall acceptance in using the ARGOS-IO system in their daily routine. The instruction for use for the Mesograph reader device was easily to understand, the implant did not cause them any problems and the patients were less concerned about unidentified high IOP.

Compatibility of the ARGOS-IO implant with Glaucoma drainage devices (GDD)

Compatibility of the ARGOS-IO implant with Glaucoma drainage devices (GDD) was an issue that was long discussed within the risk analysis team. This clinical trial showed if the GDD is placed in the anterior chamber, there is no physical contact with the ARGOS-IO implant, which is located in the ciliary sulcus, and consequently no interference occurs between the two devices.

 Implantdata Ophthalmic Products GmbH	Clinical Investigation Report ARGOS-KP01	Revision A Page 102 of 114
---	---	-----------------------------------

Overall Summary: Based on the clinical study results, risk management effort and user information, it is concluded that the benefits for a patient from the implantation of an ARGOS-IO implant device outweighs the risk. Predicate implantable ophthalmic medical devices, like Boston-Keratoprosthesis, show that there is also residual risk with regard to the surgical procedure in general. The adverse event rate by combining BKPro implantation with EYEMATE-IO/KP insertion is similar to BKPro implantation alone and adverse events were in general manageable under standard of care. **The medical benefit of the implantation of the device, and resulting possibility of direct IOP measurement and frequent self-tonometry by the patients at home clearly outweighs the identified residual risks of the device. The residual risks and their probability of occurrence are within the acceptable range, compared to similar marketed devices in the ophthalmic field.**

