3.2. Trial Design

The investigation is designed as a prospective, open-label, single-arm, early feasibility study.

The ARGOS-IO system is a non-CE marked investigational medical device composed of the implant and its accessories:

- Implant: ARGOS-IO pressure sensor implant for sulcus placement or trans-scleral fixation
- Accessories: MESOGRAPH reading device, Implant Injector

Concerning patients undergoing implantation of a Boston Keratoprosthesis (BKPro), the ARGOS-IO pressure sensor is intended to be implanted in the human eye in combination with BKPro surgery and to remain in place indefinitely. The ARGOS-IO pressure sensor is intended to be used together with the hand-held MESOGRAPH reading device to telemetrically measure the intraocular pressure (IOP) of patients with a BKPro.

The investigation will consist of 15 visits: the Screening visit, the Surgery visit (Day 0), four early follow-up visits 1, 5, 10, and 15 days after surgery and further nine follow-up visits at weeks 4, 10, 16, 22, 28, 34, 40, 46 and 52.

The Screening visit will be performed within 60 days prior to surgery.

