5.2. Adjustments for Covariates

N/A – Covariates will not be included in the statistical analyses.

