5.7. Examination of Subgroups

Subgroups will not be considered for analysis.

6. Study Population Characteristics

In general, statistical tables described in this chapter will show data separated by analysis population (safety set, per-protocol set) and for the total analysis population.

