7.4. Anterior Eye Segment Assessments

Findings of the slit-lamp biomicroscopy will be summarized overall ('any finding') and by segment (lids, conjunctiva, cornea, anterior chamber, iris, pupil, lens, aqueous humor, other) and will include the number and percentage of patients with at least one finding reported. A summary table will be

Statistical Analysis Plan

Version 1.0 [Final], 09-Jan-2018

generated on a patient level: Patients are counted only once for each segment when they have more than one finding within the segment of the anterior eye.

In addition, clinically significant findings will be summarized overall ('any finding') and by segment and will include the number and percentage of patients with at least one clinically significant finding reported. A summary table will be generated on a patient level: Patients are counted only once for each segment when they have more than one clinically significant finding within the segment of the anterior eye.

Further description of the anterior segment findings including severity will be presented in corresponding patient data listings only.

Measurements regarding the cup disc ratio, central retinal thickness and white-to-white diameters will be listed in a patient data listing.

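### The report says the trial has shown that anatomy does not affect sensor accuracy, but no planned or listed analysis relates anatomy or placement to accuracy

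*Protocol*

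**What the plan says.** Section 5.5 of the report (the protocol document) asks whether the device has acceptable accuracy and precision. Part of its answer is: "ARGOS-KP01 trial has shown that the human anatomy does not have an impact on the accuracy of the device".

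The SAP sets out what was to be analysed:

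- **Covariates (5.2):** "Covariates will not be included in the statistical analyses".
- **Subgroups (5.7, also 4.2):** "Subgroups will not be considered for analysis".
- **Tests and sites (5.6, 5.5):** no tests are planned, only description with 95% confidence intervals, and sites are pooled.
- **Performance (9.1, 9.2, 9.6):** a Bland-Altman analysis over all visits, the same by visit, an IOP summary by time point within the visit, and ARGOS readings by finger-palpation category.
- **Anatomy and placement:** axial length is a baseline summary (7.2). For white-to-white diameter, "Measurements regarding the cup disc ratio, central retinal thickness and white-to-white diameters will be listed in a patient data listing" (7.4). Lens status (8.1) and ring size, sulcus support, fixation and chip orientation (8.2) are stand-alone frequency tables.

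**The concern.** The sentence claims that an effect is absent. A claim of that kind needs an analysis that looks for the effect, and enough precision to rule out effects that matter. A pooled agreement result provides neither, because it describes the average bias and spread across whichever eyes were measured.

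Anatomy was a live question for this device. Section 1.3 of the report explains that distortion of the ciliary sulcus put radial force on the first-generation ring, and that under such force in vitro "the original ARGOS-IO pressure sensor prototype produces aberrant pressure readings". Section 4.2 gives the diversity of the patients' baseline parameters as one reason for raising enrolment. A reader of the risk/benefit section could therefore take the sentence as a tested assurance about the readings of a permanent implant.

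**Working it through.** The documents give no figure to reproduce: no formal sample size calculation (SAP 3.5), no power and no acceptance limit for agreement. The check has three steps.

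**1. Does any output relate anatomy or placement to accuracy?**

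- SAP 13.3, Tables 14.2.1 to 14.2.6 and Figures 14.2.1, 14.2.3 and 14.2.6: measurements by method, difference over time, agreement overall and by visit, device deficiencies, readings by time point, and readings by palpation category. None is broken down by an anatomical or placement variable.
- SAP 13.3, Tables 14.1.4.2, 14.1.7.1 to 14.1.7.4, 14.1.8.1 and 14.1.8.2: disease characteristics, lens, drainage device, keratoprosthesis, sensor implantation and chip orientation. None contains the ARGOS-manometry difference.
- The report's lists of tables and figures: difference plots per patient (Figures 8 to 16) and for all patients, Bland-Altman plots by visit and overall, and the palpation scatter plot. None is by anatomy or placement.

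**2. Does the text support the other natural reading, that accuracy in the human eye matched accuracy on the bench?** The visible text has no comparison of in-eye with bench accuracy and no pre-set limit of agreement. Section 5.1 also concedes that problems with manometry limit its comparability with ARGOS.

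**3. Could a trial of this size have shown absence of an effect?**

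Inputs from the documents:
- 12 patients included, 9 finished (report 5.1).
- Stated sensor accuracy of 2 mmHg, given as a 3-sigma value (report 2.2.1.1).
- Manometry omitted for hypotony and, at site DE-02, in aniridia patients after SAEs (report 4.5). Reference values are therefore missing for some abnormal eyes.

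Assumptions, not from the documents: one mean difference per patient, nine patients split 6 versus 3 on some anatomical factor, and a between-patient SD of that mean difference of 2 to 5 mmHg.

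Half-width of the 95% confidence interval for a difference in bias = t(0.975, 7 df) × SD × √(1/6 + 1/3) = 2.365 × 0.707 × SD = 1.67 × SD.

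| Assumed SD (mmHg) | Half-width (mmHg) |
|---|---|
| 2 | 3.3 |
| 3 | 5.0 |
| 5 | 8.4 |

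The half-width falls below 2 mmHg only if the SD is under 2 / 1.67 = about 1.2 mmHg.

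Two variations point the same way. With all 12 patients split 6 versus 6, the multiplier is 1.29, so the half-width is still 1.29 × 2 = 2.6 mmHg at an SD of 2. For a continuous variable such as axial length, an observed correlation of zero in 9 patients has a 95% interval of ±tanh(1.96/√6) = ±0.66. In 12 patients it is ±tanh(1.96/√9) = ±0.57.

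**The case against.** The strongest reply is that the sentence follows a bullet on bench and animal testing and may mean only that the sensor, once in a human eye, still agreed with the reference. It names no dimension, fixation or lens state. That reading is fair, but step 2 shows that the visible text does not support it as something the trial has shown either.

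Other points stand and limit the criticism:

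- **The data are not hidden behind one pooled number.** SAP 9 lists every patient's values, and the report lists individual plots: nine figures but eight distinct patient labels, since DE-2-02 appears twice. A biased eye could be seen. Seeing it is still not an analysis against anatomy.
- **An unlisted analysis is possible.** Parts of section 4.7.1 are not in the public text, and section 5.5 reports a significant difference by palpation category although the SAP planned no tests. None on anatomy appears in any list.
- **Bench evidence favours the redesign.** Section 1.3 says the new ring did not show the abnormal readings under radial force. That is relevant, but it is not a result of this trial.
- **The sentence is one bullet.** It is absent from the summary's conclusions, the performance discussion (5.3) and the overall summary in 5.5. Section 5.1 already concedes the small number of patients and their differing underlying diseases.
- **The illustration depends on an assumed split and assumed SDs.**

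Three stronger readings are tempting but not supported. First, a reader might infer that sensors were placed in several ways, since the SAP describes an "ARGOS-IO pressure sensor implant for sulcus placement or trans-scleral fixation". That entry and the fields in SAP 8.1 and 8.2 are planned categories. The visible text does not show how many eyes fell into each. Second, a reader might see a contradiction between "it is not possible to assess the effects of the design modification in animals" (1.3) and "Accuracy, precision and sensor drift have been tested and validated in bench tests and in animal trials" (5.5). The first concerns the effect of the redesign, which depends on fit in the human eye. The second concerns accuracy, precision and drift. Both can be true. Third, the advice to re-calibrate yearly and after ocular surgery might seem to refute the sentence. It is equally consistent with sensor drift and says nothing about differences between eyes.

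**Conclusion.** The concern holds as a point about an unsupported conclusion. No planned or listed analysis relates anatomy or placement to the ARGOS-manometry difference, so the trial has not shown that anatomy has no effect on accuracy, under either reading of the sentence. This rests on the SAP, its output list and the report's own lists, with the reservation that part of the performance results is not visible.

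The size argument is illustrative. For SDs of 2 to 5 mmHg and a 6 versus 3 split, a difference in bias of 3.3 to 8.4 mmHg either way would be compatible with a null finding. Only an SD below about 1.2 mmHg would bring the half-width under the stated 2 mmHg sensor accuracy.

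The documents do not show that anatomy does affect accuracy, that any particular group of eyes was biased, or that the primary agreement analysis is wrong. The defect is confined to one statement in the risk/benefit section.

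**What to change.** In section 5.5, delete the sentence. Alternatively, replace it with the observed agreement (bias, limits of agreement with confidence intervals, number of eyes and number of measurement pairs) and a statement that the effect of anatomy and placement on accuracy was not assessed.

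Optionally, extend Listing 16.2.6.1 to show each patient's mean ARGOS-manometry difference beside ring size, fixation, sulcus support, lens and iris status, and site. Because the SAP was final in January 2018 and the outputs are dated February 2018, this must be labelled post hoc and descriptive. With about nine eyes and several factors it can flag an outlying eye but cannot support a conclusion either way.

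The wording change needs no new data, and the listing needs only a few extra columns. The price is that one conclusion becomes less favourable.

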3.3.3.11 Intraocular pressure (IOP) measurement

Intraocular pressure (IOP) was measured using four techniques. To provide a baseline IOP measurement, both Goldmann Applanation Tonometry (GAT) and pneumotonometry were performed at V01 (screening) if possible. Beginning at V03 (first follow-up visit), IOP measurement was performed with the ARGOS-IO system, both by site personnel at clinic visits and after discharge

 Implantata Ophthalmic Products GmbH	Clinical Investigation Report ARGOS-KP01	Revision A Page 37 of 114
--	---	----------------------------------

from hospital by the subject at home between visits. Direct manometry was performed at visits 07, 09, 11 and 15 to allow assessment of the accuracy of the ARGOS-IO system.

After surgery, treatment decisions was based on direct manometry, supplemented by finger palpation.

IOP measurement in the clinic

On the occasions when IOP was measured with both ARGOS-IO and manometry, it was measured as a series consisting of first with ARGOS-IO prior to positioning of the operating microscope, then manometry and followed again by ARGOS-IO. At the other follow-up visits IOP was measured with ARGOS-IO at least two times at every visit preferably at the beginning and end of the visit.

The surgical manometry measurements was conducted in the surgical suite under an operating microscope. A manometry system utilizing sterile saline solution was implemented via a 21-gauge needle cannulated to the anterior chamber. A standard procedure was followed both during the preparation of the system and the measurement in order to minimize the possibility of leaks or trapped air in the system.

At follow-up visits where manometry was not performed, the physician also estimated IOP using finger palpation, categorizing pressure as soft/hypotonic, definitely normal, borderline or definitely hypertonic.

ARGOS-IO system measurement by the subject at home

While in the clinic following surgery, subjects received detailed instruction in the use of the Mesograph reading device. Upon discharge from the clinic, they received an individual Mesograph reading device, a copy of the instructions for use and the Multiline Connector to perform self-tonometry at home. Subjects were requested to perform at least 4 IOP measurements with the Mesograph daily, evenly spread throughout the day.

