4.7 Performance

4.7.1 Tonometry

4.7.1.1 ARGOS-IO System

Telemetric IOP assessments by the ARGOS-IO implant was conducted at every study visit of every patient.

In the following line graphs (Figure 6) display the individual ARGOS-IO measurements over per patient at scheduled visits. Post-operative study visits were at Day 1, 5, 10, 15 and week 4, 10, 16, 22, 28, 34, 40, 46 and 52.

Figure 6. Individual IOP follow-up during study period per patient measured with the ARGOS-IO system

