5.4 Relevance of the Results in the Light of Previous / External Data

The ARGOS-IO device performed well in patients with a Boston Keraprosthesis and showed an overall good consistency between the telemetric IOP and finder palpation/manometry. Though the implantation of the ARGOS-IO device in conjunction with the BKPro might pose additional risks compared to stand-alone BKPro implantation, the complications observed where found to be in the range of the occurrences reported in the literature. Considering the high prevalence of preexisting glaucoma in patients undergoing the Boston Keratoprosthesis surgery (Ahmad S. M. P., 2016) and the Glaucoma progression after implantation of the BKPro (de Oliveira L. A., 2014) (Samarawickrama C., 2018), the implantation of a monitoring device (ARGOS-IO) clearly outweighs the risks induced by implantation of an additional device within the same surgical procedure.

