5.5 Risk / Benefit Assessment

Glaucoma is the most significant cause of the loss of regained vision in keratoprosthesis recipients. Reduction of IOP is to date the only proven therapy for glaucoma (Quigley, 2011). Improved control of IOP is linked to better long-term outcomes for glaucoma patients (King, Glaucoma, 2013).

The presence of BI-KPro does not allow conventional tonometric IOP measurement, as this requires a normal cornea. Patient self-monitoring or home measurement is also not possible, as available devices are also using tonometric IOP measurement methods. Currently, surgical manometry – if properly performed – is the only accurate means of measuring IOP in BKPro recipients. But due to its invasiveness and risk for complications, most ophthalmologists don't perform surgical manometry at BI-KPro patients. Equipment for surgical manometry is in general not available either, which is another reason why invasive IOP measurements are performed only in very rare cases. Usually finger

 Implantata Ophthalmic Products GmbH	Clinical Investigation Report ARGOS-KP01	Revision A Page 100 of 114
--	---	-----------------------------------

palpation is applied to estimate IOP, but is highly dependent on the skill of the individual examiner, provides highly subjective values and thus prone to error.

IOP in BI-KPro patients can be extremely high, potentially causing severe glaucomatous damage in unusually short periods of time. Even a comprehensive follow-up schedule may not be appropriate. This problem is compounded if no physician experienced in the finger palpation technique is available to perform IOP estimation.

The ARGOS-IO device allows frequent, reproducible IOP monitoring in both the clinical and home setting, facilitating the management of IOP in this vulnerable patient group. In addition, because of the ease of its use, it will also permit detection of fluctuations in IOP resulting from the patient's daily activities and circadian rhythm.

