CRO	Contract research organization
eCRF	Electronic case report form
FSI	First patient in
ICH	International Conference on Harmonization
IMD	Investigational medical device
IOP	Intra-ocular pressure
LSO	Last patient out
MedDRA	Medical Dictionary for Regulatory Activities
N/A	Not applicable
PPS	Per Protocol Set
SAE	Serious adverse event
SAP	Statistical Analysis Plan
SAS	Statistical Analysis System
SFS	Safety Set
SOC	System Organ Class
TFLs	Tables, Figures and Listings
WHO	World Health Organization
WHO-DDE	WHO-Drug dictionary enhanced

Statistical Analysis Plan

Version 1.0 [Final], 09-Jan-2018

1. Introduction

This Statistical Analysis Plan (SAP) is based on the final Protocol for the clinical investigation ARGOS-KP01 and its final eCRF.

Aim of this SAP is to determine prospectively the analysis strategy of this clinical investigation and to describe the methods used for the final analysis. The statistical evaluation of all eCRF parameters as well as other data sources will be performed by the CRO X-act Cologne Clinical Research GmbH (X-ACT) according to this SAP.

This SAP is developed in one step and will be agreed on as final version before the Database Lock.

2. Changes from Protocol including Amendments

- Analysis of Questionnaires and daily IOP self-measurement profiles (patients) will not be performed (not databased)
- Performance analysis will also be done on the Safety Population
- No subgroup analyses will be performed

There are no other changes in the statistical evaluation as compared to the final Clinical Investigation Protocol.

3. Study Overview**3.1. Trial Objective(s)**

The primary objectives of this clinical investigation are:

- Safety: To evaluate the safety and tolerability of the ARGOS-IO pressure sensor in the 12 months following implantation.
- Performance: To evaluate the performance of the ARGOS-IO system compared to manometry in the 12 months following implantation

The secondary objectives of this clinical investigation are:

- Safety: To evaluate the safety and tolerability of the ARGOS-IO pressure sensor use in the first 4, 16 and 28 weeks after implantation.
- Performance: To compare the IOP measured with the ARGOS-IO system to that obtained with manometry at weeks 4, 16 and 28 after implantation.

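### Section 5.5 states home monitoring and a similar event rate to keratoprosthesis alone without the limits of a single-arm study of 13 patients whose home pressure profiles were not analysed

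*Protocol*

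**What the plan says.** The document filed as the protocol is a clinical investigation report. The synopsis describes a single-arm safety and performance study. Its control is a second measurement method, surgical manometry in the same eye, and not a second group of patients. SAP section 3.5 reports no formal sample size calculation, and SAP section 5.6 plans no tests, only descriptive results with 95% confidence intervals. Twelve patients received the implant; the safety set has 13.

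**Risk side.** The Overall Summary in section 5.5 says that the event rate of the combined procedure "is similar to BKPro implantation alone and adverse events were in general manageable under standard of care". Section 5.4 concludes that "the implantation of a monitoring device (ARGOS-IO) clearly outweighs the risks induced by implantation of an additional device", citing literature on glaucoma in these patients.

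**Benefit side.** The Overall Summary holds that the "resulting possibility of direct IOP measurement and frequent self-tonometry by the patients at home clearly outweighs the identified residual risks of the device". It names study results, risk management and user information as its bases. Earlier in section 5.5 stands: "The ARGOS-IO device allows frequent, reproducible IOP monitoring in both the clinical and home setting".

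**Home readings.** Section 3.3.3.11 sets the task: "Subjects were requested to perform at least 4 IOP measurements with the Mesograph daily, evenly spread throughout the day". Daily home profiles are a secondary performance endpoint in section 3.1.3.2 and in SAP section 3.4.2. SAP section 2 then lists this change: "Analysis of Questionnaires and daily IOP self-measurement profiles (patients) will not be performed (not databased". Section 4.6 leaves home readings out of the per-protocol agreement evaluation because they are not expected to be comparable with clinic readings. Figure 6 consists of line graphs that "display the individual ARGOS-IO measurements over per patient at scheduled visits".

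**Use of the readings.** Section 3.3.3.11 also says: "After surgery, treatment decisions was based on direct manometry, supplemented by finger palpation".

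**The concern.** Section 5.5 is where a reader deciding about implantation will look. It would be natural to take two things from it as findings of this trial: that adding the sensor leaves the complication rate unchanged, and that patients obtain reproducible pressure readings at home.

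The first needs either a concurrent keratoprosthesis-alone group or an external comparison precise enough to rule out a meaningful increase. The second needs an analysis of home readings. If neither exists, both statements should carry that limit. Section 5.1 lists small numbers, short follow-up and the difficulties of manometry. It mentions neither the missing comparator nor the unanalysed home profiles.

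**Working it through.** **1. The report's own figures reproduce.** Section 4.8.1 gives 92 events unlikely to be device-related, 61 unrelated and 15 possibly related: 92 + 61 + 15 = 168, the stated total. Table 11 gives 4 of 13 patients with an adverse device effect: 4/13 = 30.8%, as printed.

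**2. Event rates with the planned interval.** The report and SAP section 5.1 name the two-sided Clopper-Pearson 95% interval. For x of n patients, the lower limit is the 0.025 quantile of Beta(x, n − x + 1) and the upper limit is the 0.975 quantile of Beta(x + 1, n − x). Patient counts come from Table 9 and are all-cause, because a rate after keratoprosthesis alone cannot be restricted to sensor-related events. Reference rates are those cited in section 4.8.1.

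| Event | x/n | Rate | Exact 95% CI | Cited stand-alone rate |
|---|---|---|---|---|
| Cystoid macular edema | 3/13 | 23.1% | 5.0% to 53.8% | up to 27% |
| Vitritis | 4/13 | 30.8% | 9.1% to 61.4% | up to 23% (aniridia patients) |
| Retroprosthetic membrane | 6/13 | 46.2% | 19.2% to 74.9% | more than 50% |

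Every interval contains the cited figure (taking 50% for the last). Every interval also reaches well above it.

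**3. How large an excess could pass unnoticed.** This is an illustration: the excess risks are my assumptions, and the SAP plans no test. Take n = 13, a fixed reference rate p0 and an exact one-sided test at 2.5%. The smallest number of patients that rejects is 7 for p0 = 23%, 8 for 27% and 11 for 50%. Power is P(X ≥ critical value) at p0 plus the excess:

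| Reference | +10 points | +20 points | +30 points |
|---|---|---|---|
| 23% | 0.099 | 0.303 | 0.587 |
| 27% | 0.064 | 0.220 | 0.485 |
| 50% | 0.058 | 0.202 | 0.502 |

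Even a true excess of 20 points would usually not stand out.

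**4. Primary safety endpoint.** The summary of results says that 15 possibly related events occurred in four patients and that six were serious. The text available to me does not give the number of patients with a serious device-related event. It must lie between 1 and 4, so the planned interval lies between that for 1/13 (7.7%; 0.2% to 36.0%) and that for 4/13 (30.8%; 9.1% to 61.4%). The sponsor has the exact count for SAP Table 14.3.1.1.

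**5. Evidence for home use.** The profiles were a planned secondary endpoint, were dropped in SAP section 2, and have no entry in SAP sections 13.3 and 13.4. The report's table of contents and lists of tables and figures show no home-profile analysis. Clinic agreement cannot stand in for it, given section 4.6. What remains from this trial is the patient acceptance questionnaire in section 4.7.2, with N = 6. All six would consider permanent home use: 6/6, 95% CI 54.1% to 100%, where the lower limit is 0.025^(1/6). That measures acceptance, not reproducibility.

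**The case against.** **The benefit is worded as a capability.** A reader might infer that section 5.5 claims proven clinical benefit and that its favourable balance is therefore unsupported. The documents do not bear that out. The Overall Summary speaks of a possibility of measurement, and better adherence and pressure control are described as expected. Basing treatment on manometry and palpation was a sensible safeguard for an unproven device. Objecting to the word *clearly* alone would be a matter of tone.

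**Other evidence is named.** Section 5.5 cites risk management, user information, and bench and animal tests of accuracy and drift. Section 1.3 describes ARGOS-01, where patients used an earlier version easily at home, and the 22-patient ARGOS-02 study behind the CE approval. The home-monitoring sentence is not explicitly tied to this trial's readings. That stands, but the sentence names no source and sits in this trial's risk/benefit assessment.

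**The limits are partly disclosed.** Section 5.1 admits small numbers, section 5.2 that causality cannot be clearly separated between the two implants, section 5.4 that the sensor might add risk, and section 4.8.1 a possibly increased likelihood of device effects. These are fair disclosures, but the Overall Summary does not carry them into its statement about the event rate.

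**SAP silence is weak proof.** The SAP line that drops the profiles also drops the questionnaires, yet patient questionnaire results are reported, and part of the tonometry results was not in the text available to me. The report's own contents and figure lists are the better evidence.

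**Added harm or lost data.** A reader might infer from vitritis at 30.8% against 23% that the sensor raises risk. The interval includes 23%, and the reference covers aniridia patients only. A reader might also turn four readings a day into a large count of lost data. The documents give no actual count, so such a figure measures nothing.

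**Conclusion.** Two statements in section 5.5 need limiting. Similarity to keratoprosthesis alone rests on published rates set against 13 patients. The three intervals (5.0% to 53.8%, 9.1% to 61.4%, 19.2% to 74.9%) allow no increase and a large one. Reproducible home monitoring is not shown by this trial, which supports home use through six acceptance questionnaires only.

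This is a fault of inference and wording. The single-arm descriptive design is openly stated, and nothing here invalidates the agreement or safety results. The conclusion assumes that the cited rates can be taken as fixed (their sources were not checked), that all-cause counts are the like-for-like comparison, and that no home-profile analysis stands in the results text that I could not see.

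**What to change.** 1. In the section 5.5 Overall Summary, replace the similarity statement with: *is compatible with published rates for BKPro alone; with 13 patients and no concurrent comparator, an increase cannot be excluded*.
2. At the home-monitoring statement in section 5.5 and in the Overall Summary, say that the daily home profiles were not analysed, that this trial therefore supports home use by acceptance questionnaires (N = 6) only, and that clinical benefit from acting on the readings is expected, not shown by this trial. If reproducibility is claimed from bench work or another study, name that source.
3. Add the missing comparator and the unanalysed home profiles to section 5.1.
4. Where the balance is stated, give the planned exact interval for the primary safety endpoint, patients with a device-related serious event (SAP section 10.1, Table 14.3.1.1). The 4/13 interval for any adverse device effect may be added but should not stand alone. Neither interval measures risk relative to keratoprosthesis alone.

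The cost is report wording: no new data are needed, and the interval is already a planned output. The conclusion becomes slightly less favourable to the device.
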